4.11.2.10 Analysis of Infusion-Related Reactions

In the AE eCRF page, an option is provided whether AE is infusion-related or not. Based on that we will have a pre-defined list of IRRs using selected PTs from MedDRA.

Separate summaries of the number of subjects with infusion-related reactions and non-infusion related reactions AEs will be provided by SOC and PT including the number and percentage of subjects experiencing events.

Subgroup analysis will also be performed for infusion-related and non-infusion related reactions by CCI index by SOC and PT including the number and percentage of subjects experiencing events.

Subgroup analysis will also be performed for infusion-related and non-infusion related reactions by tumor grades CCI index by SOC and PT including the number and percentage of subjects experiencing events.

Subgroup analysis will also be performed for infusion-related and non-infusion related reactions by geographical region by SOC and PT including the number and percentage of subjects experiencing events.

A by-subject listing of infusion-related reactions will be provided, including both AEs and non-AEs.

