6.2.1 Study Drug Infusion Preparation

Study drug (DRL_RI or MabThera[®]) solutions for infusion will be prepared by an unblinded pharmacist/authorised designee/unblinded qualified physician in this study. Unblinded pharmacist/authorised designee/unblinded qualified physician should use aseptic techniques appropriate to parenteral administration products.

Study drug will be administered by i.v infusion by blinded study personnel. Study drug vials and prepared solutions should be inspected visually for particulate matter and discoloration prior to administration. Do not use vials if particulates or discoloration are present.

6.2.2 **Pre-Medication for Study Drug Infusions**

All subjects should receive pre-medication with 100 mg i.v methylprednisolone or their equivalent to be completed at least 30 minutes prior to rituximab infusions to decrease the incidence rate and severity of acute IRRs. Pre-medication consisting of an anti-pyretic and an antihistamine (e.g., paracetamol [acetaminophen] and diphenhydramine), should always be administered before each infusion of rituximab.

Acute IRRs are most often observed during the first infusion of rituximab. Any reduction in use of pre-medications during subsequent infusions must be in compliance with local labelling and regulation.

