6.2.3 Study Drug Administration

Study drug (DRL_RI or MabThera[®]) will be administered by i.v infusion using the escalating infusion rate in accordance with the EMA approved labelling for MabThera[®]. The infusion rate must be well controlled to reduce the incidence of serious IRRs.

Only qualified personnel who are familiar with procedures that minimise undue exposure to them and to the environment should undertake the preparation, handling, and safe disposal of study drugs.

The study drug infusion must be administered in the presence of the Investigator/medically qualified study site staff (to enable compliance), and in an environment where full resuscitation facilities are immediately available. Vital signs will be monitored every 30 minutes during the course of the treatment administration and at the end of infusion or more frequently as necessary.

The study drug will be administered at a dose of 375 mg/m^2 of BSA. Subjects will receive induction treatment consisting of weekly i.v infusions for 4 weeks, followed by maintenance treatment consisting of an i.v infusion every 8 weeks from Week 12 up to Week 36.

The instructions below should be followed in conjunction with the local product labelling if it differs from these instructions. An electronic infusion pump is required to be used.

- First Infusion (Day 1): Initiate infusion at a rate of 50 mg/hour. In the absence of infusion toxicity, increase infusion rate by 50 mg/hour increments every 30 minutes, to a maximum of 400 mg/hour.
- Subsequent Infusions: Initiate infusion at a rate of 100 mg/hour. In the absence of infusion toxicity, increase rate by 100 mg/hour increments at 30-minute intervals, to a maximum of 400 mg/hour.
- Subjects should be closely monitored for the onset of cytokine release syndrome. Subjects who develop evidence of severe reactions, especially severe dyspnoea, bronchospasm or hypoxia should have the infusion interrupted immediately. In all subjects, the infusion should not be restarted until complete resolution of all symptoms, and normalization of laboratory values relating to the infusion reaction. At this time, the infusion can be initially resumed at not more than one-half the previous rate. If the same severe adverse reactions occur for a second time, the decision to stop the treatment should be seriously considered on a case by case basis.

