4.11.2 Analysis of Adverse Events

All reported terms for AEs will be coded using the latest version of MedDRA version 21.1 or the latest. Before database lock the latest version of MedDRA will be used to code the AE terms for all study subjects. The US National Cancer Institute (NCI) Common Terminology Criteria for Adverse Events (CTCAE), version 5.0 (NCI-CTCAE version 5.0) will be used by investigator to assess the severity grade of all AEs.

For all AE tables, subjects will be counted once for each MedDRA PT and each SOC. Unless specified otherwise, AEs will be summarized in the alphabetical order of SOC and then decreasing frequency of PT within the SOC for the treatment group. If the frequency of PT within the SOC is tied, PT will be sorted alphabetically. Summaries by PT will be sorted by decreasing frequency according to the "DRL_RI" subject incidence.

TEAEs are defined as any AE occurring or worsening on or after the first dose of study treatment. AEs which are already present before the first study treatment and increase in severity after the first study treatment will be considered as TEAEs. Pre-existing AEs before the first study treatment with no increase in severity after the first study treatment will not be considered as TEAEs.

All treatment-emergent adverse events (TEAEs) will be summarized by SOC, PT and CTCAE grade, including the number and percentage of subjects experiencing events.

An overview of AEs by treatment group will be provided, including number of subjects experiencing TEAEs, drug related TEAEs, serious TEAEs, drug related serious TEAEs, TEAEs leading to discontinuation of study medication, drug related TEAE leading to discontinuation of study medication, TEAEs leading to death,. The summary will also be provided for subgroups age group (< $60, \ge 60$ years), gender and race.

Imputation of partial dates of AE record is described in Appendix 2 Partial Date Conventions.

[name] S.A	
Protocol RI-01-006	Statistical Analysis Plan

A by-subject listing of all AEs will be provided by treatment group and will include AE term (SOC, PT, and Verbatim term), start date/time and corresponding study day, end date/time and corresponding study day, severity, infusion related reaction (yes/no), relationship, action taken, outcome, seriousness including criteria of serious adverse event (SAE).

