4.11.2.2 Analysis of Treatment-Emergent Adverse Events

A summary of the number of subjects with drug related TEAEs by SOC, PT including the number and percentage of subjects experiencing events, separately. TEAEs with incidence by $PT \ge 5\%$ in either of DRL_RI or MabThera treatment group will be additionally summarized by SOC, PT and CTCAE grade by treatment group.

A summary of TEAEs observed, based on the onset date, during the rituximab induction and maintenance will be summarized separately by treatment groups.

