4.11.2.3 Analysis of TEAEs by Severity

A summary of the number and percentages of subjects with TEAEs, number of events will be provided by SOC, PT and by CTCAE grade including the number and percentage of subjects experiencing events. If same event occurred more than once in the same subject, the highest severity grade will be used for the analysis.

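### The SAP plans no infusion-reaction summary by first versus later infusion or by maximum grade; one extra table would close the gap

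*SAP*

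**What the plan says.** Comparing safety and tolerability is a secondary objective (Protocol 3, SAP 2.2), and the incidence of infusion reactions in each arm is a named safety endpoint (Protocol 9.4.2).

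- **IRR tables.** SAP 4.11.2.10: "Separate summaries of the number of subjects with infusion-related reactions and non-infusion related reactions AEs will be provided by SOC and PT". The section repeats them by risk index, tumour grade and region and adds a by-subject listing. It has no split by infusion, treatment period or grade.
- **Counting rule.** SAP 4.11.2: "For all AE tables, subjects will be counted once for each MedDRA PT and each SOC".
- **Schedule.** Protocol 6.2.3: "induction treatment consisting of weekly i.v infusions for 4 weeks", then "treatment consisting of an i.v infusion every 8 weeks from Week 12 up to Week 36".
- **When reactions occur.** Protocol 6.2.2: "Acute IRRs are most often observed during the first infusion of rituximab".
- **General tables.** SAP 4.11.2.2: "A summary of TEAEs observed, based on the onset date, during the rituximab induction and maintenance will be summarized separately by treatment groups". SAP 4.11.2.3: "A summary of the number and percentages of subjects with TEAEs, number of events will be provided by SOC, PT and by CTCAE grade". Neither is restricted to IRRs.

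**The concern.** A subject who reacts at infusion 1 already counts in the IRR table. A second reaction with the same preferred term at Week 12 changes nothing there. If first-infusion reactions are common and alike in both arms, they form a background that shrinks any contrast arising later. The protocol itself treats the first infusion differently: Protocol 6.2.3 starts it at a different rate, and Protocol 6.2.2 contemplates reduced pre-medication afterwards. The ever-affected count therefore pools unlike exposures.

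At stake is the sensitivity of one descriptive comparison, on a harm that the plan names as an endpoint.

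**Working it through.** **1. Number of infusions.** Weeks 1 to 4 give 4. Weeks 12, 20, 28 and 36 give 4. Total 8, of which 7 follow the first.

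**2. Which planned output shows what.**

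| Output | IRR-specific | Infusion 1 apart from 2–4 | Induction vs maintenance | Grade |
|---|---|---|---|---|
| IRR tables, SAP 4.11.2.10 | yes | no | no | no |
| TEAEs by period, SAP 4.11.2.2 | no | no | yes | no |
| TEAEs by severity, SAP 4.11.2.3 | no | no | no | yes |
| Dose interruptions etc., SAP 4.11.1 | no | no | yes | no |
| AE and exposure listings, SAP 4.11.1 and 4.11.2 | flag shown | by date and time | by date | yes |

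No table fills the first two columns together. None counts subjects with any IRR by maximum grade.

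**3. Size of the dilution.** The plan states no IRR rate or power to reproduce, so every rate below is assumed. Let f be the chance of an IRR at infusion 1 (equal in both arms) and L the chance of at least one at infusions 2–8. If the two are independent, ever-affected = f + (1 − f)L. The between-arm difference is then (1 − f) times the later-infusion difference.

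Simple case, n = 156 per arm (SAP 4.13.2), f = 40%, L = 5% vs 12%:
- Ever-affected: 0.40 + 0.60 × 0.05 = 43.0%, and 0.40 + 0.60 × 0.12 = 47.2%. Difference 4.2 points; SE = √[(0.430 × 0.570 + 0.472 × 0.528)/156] = 5.63 points; z = 0.75. Chance that a 95% CI excludes 0: about 12%.
- Infusions 2–8: difference 7 points; SE = √[(0.05 × 0.95 + 0.12 × 0.88)/156] = 3.13 points; z = 2.23. Chance: about 61%.
- With f = 30% and L = 3% vs 10%, the two chances are about 15% and 72%.

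Per-infusion model: l is the chance at each later infusion, so L = 1 − (1 − l)^7, and maintenance is 1 − (1 − l)^4. Brackets give the ratio between arms, from unrounded rates, and the two-sided 5% power.

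| f | l | Ever-affected | Infusions 2–8 | Maintenance |
|---|---|---|---|---|
| 15% | 1% vs 3% | 20.8 vs 31.3% (1.51; 56.5%) | 6.8 vs 19.2% (2.83; 90.7%) | 3.9 vs 11.5% (2.91; 70.5%) |
| 25% | 1% vs 3% | 30.1 vs 39.4% (1.31; 40.7%) | as above | as above |
| 40% | 1% vs 3% | 44.1 vs 51.5% (1.17; 25.9%) | as above | as above |
| 15% | 2% vs 5% | 26.2 vs 40.6% (1.55; 77.4%) | 13.2 vs 30.2% (2.29; 95.7%) | 7.8 vs 18.5% (2.39; 80.8%) |
| 25% | 2% vs 5% | 34.9 vs 47.6% (1.36; 62.8%) | as above | as above |
| 40% | 2% vs 5% | 47.9 vs 58.1% (1.21; 43.7%) | as above | as above |

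**4. Dependence.** If later reactions occur only in subjects who reacted at infusion 1, the ever-affected difference is 0. If they occur only in the others, ever-affected = f + L and the difference in points is undiluted. Independence lies between.

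**The case against.** A reader might infer that IRRs are reported only as ever-affected counts, so that later reactions and severity are hidden. The documents do not support that.

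- A reaction at infusion 1 and another at Week 12 can appear in both halves of the induction/maintenance table.
- The severity table gives numbers of events as well as subjects, and uses the highest grade when an event recurs.
- Serious TEAEs (SAP 4.11.3.1), TEAEs leading to discontinuation (SAP 4.11.2.6) and TEAEs by anti-drug-antibody result (SAP 4.11.2.8) are tabulated. Vital signs are summarised at time points during each infusion visit (SAP 4.2.6, 4.11.5).
- The listings carry the IRR flag, grade and start time, and the DMC reviews IRRs (SAP 4.11.10).

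All of this stands, and severity is the weaker half of the point. What remains is narrower. The general tables put IRR-flagged and other events under the same preferred term. If the pre-defined list of preferred terms mentioned in SAP 4.11.2.10 governs, the mixing matters less, because those terms can be read off the general tables. But a subject with two terms appears in two rows, so the rows cannot be summed to subjects with any IRR, and infusion 1 still sits with infusions 2–4.

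It is also fair that the protocol promises only the incidence of infusion reactions by arm, which the SAP delivers. The addition improves the plan; it does not repair a broken commitment.

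A second tempting inference is that a product difference linked to re-exposure or anti-drug antibodies would appear at later infusions, so the arms will look alike. The documents state no such mechanism; they say only that the first infusion has most of the acute reactions.

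**Conclusion.** The point holds as a low-cost improvement to a descriptive safety comparison. The dedicated IRR tables give neither first versus later infusion nor maximum grade, and the other planned outputs supply these only indirectly.

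In the assumed per-infusion cases a later-infusion ratio of 2.3 to 2.8 falls to 1.2 to 1.6, and power falls from 91–96% to 26–77%. These figures rest on assumed rates, independence between infusions, no dropout from 156 per arm, and a difference placed wholly after infusion 1. A difference at infusion 1 itself would show in the existing tables. The power figures are only a yardstick, because the plan specifies no between-arm test or CI for adverse events.

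**What to change.** Add one table, and a sentence announcing it, to SAP 4.11.2.10:

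- Columns by arm; rows for infusion 1, infusions 2–4, and maintenance overall.
- Denominator: subjects dosed in that row.
- Content: number and percentage with any IRR, and by maximum CTCAE grade, using the same IRR definition as the existing tables.
- A descriptive between-arm difference with 95% CI for infusion 1 and for all later infusions combined.
- Keep the existing tables by system organ class and preferred term.

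The IRR flag, event start time, grade and infusion times are already recorded (SAP 4.9, 4.11.1, 4.11.2), so nothing new is collected and patient management does not change. The cost is one table. Maintenance counts will be sparse, which is why separate rows for each maintenance infusion are not suggested.

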4.11.3 Analysis of Deaths, Serious Adverse Events, and Other Significant Adverse Events

4.11.3.1 Analysis of Serious Adverse Events

Serious TEAEs will be summarized by SOC, PT including the number and percentage of subjects, number of events experiencing events by treatment group.

A summary of related serious TEAEs will be provided by SOC, PT including number and percentages of subjects experiencing events, number of events by treatment group.

A summary of the number of subjects with serious TEAE outcome into "Not recovered/ Not resolved", "Recovered/ Resolved", "Recovered/Resolved with sequelae/ resolved with sequelae", "Recovering/ Resolving", "Fatal", and "Unknown" categories for number of events by treatment group and overall will be provided.

A by-subject listing of SAEs will be provided.

[name] S.A Protocol RI-01-006

4.11.3.2 Analysis of Deaths

Death and primary cause of death will be summarized by the number and percentage of subjects experiencing events by treatment group.

A by-subject listing of deaths will be provided.

4.11.3.3 Analysis of Events of Special Interest

COVID-19 events in the study are to be considered as Events of Special Interest (EOSIs).

Following summaries will be provided for EOSIs:

- Treatment emergent EOSI will be summarized by SOC, PT including the number and percentage of subjects, number of events experiencing events by treatment group. The same summary will be repeated for non-treatment emergent EOSI.
- Number and percentages of subjects with EOSIs, number of events will be provided by SOC, PT and by severity (mild, moderate, severe, life threatening, leading to death) including number and percentage of subjects experiencing events by treatment group. This summary will be repeated for Treatment emergent and Non-Treatment emergent EOSIs.
- Number of subjects with EOSIs leading to discontinuation of study medication by SOC, PT including number and percentage of subjects experiencing events by treatment group. This will be repeated for repeated for Treatment emergent and Non-Treatment emergent EOSIs.
- EOSIs leading to death by SOC, PT including number and percentage of subjects experiencing events by treatment group. This will be repeated for Treatment emergent and Non-Treatment emergent EOSIs.
- SAEs of special interest by SOC, PT including number and percentage of subjects, number of events experiencing events by treatment group.

4.11.4 Analysis of Clinical Safety Laboratory Data

Clinical safety laboratory data includes hematology, biochemistry, coagulation, and urinalysis and other screening tests. For details of clinical safety laboratory tests, refer to study protocol section 8.3.4.

Clinical safety laboratory data will be summarized for each test by visit and according to maximum NCI-CTCAE grade by treatment group. Change from baseline will also be summarized by visit and treatment group.

The shift table will summarize baseline CTCAE grade versus the worst on-treatment CTCAE grade. For a laboratory test for which an NCI CTCAE scale does not exist the shift table will be summarized using the categories

- L for values below the lower limit of the reference range
- N for values within the reference range
- H for values above the upper limit of the reference range.

A by-subject listing will be provided for laboratory parameters with absolute values by treatment group and overall, with indicator of CTCAE grade if applicable. Subjects with any out of reference range value during the study will be flagged on the listing using the following codes L, N, H as defined above.

The list of laboratory assessments to be included in the outputs is referred to

[name] S.A	
Protocol RI-01-006	

Appendix 3 Laboratory Assessments. Lab values will be converted to standard unit, as reference in the NCI-CTCAE. For white blood cell (WBC) differentials when only percentages and total leukocyte count are available the absolute values are calculated by multiplying the total number of WBCs by the percentage of each type of WBC and dividing by 100.

4.11.5 Analysis of Vital Signs

Vital signs will include heart rate, blood pressure, respiratory rate, and oral or tympanic body temperature. The results of each scheduled assessment of vital signs, actual and change from baseline values will be summarized at all post-baseline visits by treatment group.

Shift Tables for the transition from baseline among the different categories in the low/normal/high categories will be provided by treatment group, see Appendix 4 Reference Ranges for Vital Signs for definition of categories low/normal/high.

A by-subject listing of vital signs will be provided.

4.11.6 Analysis of Physical Examinations

Body weight, and body system will be summarized by treatment group for scheduled time points using descriptive statistics.

Physical examination findings will be summarized by treatment for scheduled time points using frequency tables.

A by-subject listing of physical examinations will be provided.

4.11.7 Analysis of 12-Lead Electrocardiogram

A summary of actual and change from baseline values of 12-lead electrocardiogram (ECG) data at scheduled visits will be provided by treatment group.

A summary of subjects with designated changes in VR and QT, QTcF, PR, QRS and RR will be provided by treatment group.

A by-subject listing of 12-lead ECG data and findings will be provided.

4.11.8 Analysis of ECOG Performance Status

A summary of ECOG performance status at scheduled visits will be provided by treatment group. The ECOG shift from baseline to highest score during the on-treatment period will also be summarized with categories 0, 1, 2 etc.

A by-subject listing of ECOG performance status will be provided.

4.11.9 Analysis of Immunogenicity Data

Immunogenicity data, i.e., ADA (binding antibodies (BAb)) and neutralizing antibodies (NAb) will be summarized and analyzed descriptively for each scheduled time point (baseline, Week 4, Week 8, Week 28, Week 44 and Week 52/EOS or ET):

- Number and percentage of subjects with ADA (binding antibodies (BAb)) results (positive or negative) by treatment group and visit; for positive subjects, titer values will be summarized.
- Number and percentage of subjects with NAb results (positive or negative) will be presented by treatment group and visit.

[name] S.A	
Protocol RI-01-006	Statistical Analysis Plan

A by-subject listing of immunogenicity data will be provided.

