- ^{20.} Samples for detection of BAb and NAb will be collected before the administration of study drug infusion on Day 1 and Day 22. Additional samples for detection of BAb and NAb will be collected prior to study drug infusion at Weeks 8 and 28, as well as at the visits of Week 44 and Week 52 (EOS/ET Visit).
- ^{21.} COVID-19 testing (RT-PCR, Rapid Antigen test or test with similar nature antigen test but no antibody test) to be performed as close as possible but no more than 4 days before first dose administration. COVID-19 testing may be repeated at the discretion of the Investigator. Subjects should be randomised only after negative COVID-19 test result.

2 Introduction

Rituximab is approved for use in B-cell non-Hodgkin's Lymphoma (NHL), chronic lymphocytic leukaemia, rheumatoid arthritis (RA) in combination with methotrexate in adults with moderatelyto severely-active RA who have inadequate response to one or more tumour necrosis factor antagonist therapies, and granulomatosis with polyangiitis and microscopic polyangiitis in combination with glucocorticoids.^{1,2} Rituxan[®] is the commercially available innovator reference product in the United States (US); MabThera[®] is the commercially available innovator reference product in the European Union (EU). In Japan the commercially available product is Rituxan[®]. The proposed rituximab biosimilar (hereafter referred to as DRL_RI) is being developed as a potential biosimilar to Rituxan[®] and MabThera[®]. Rituximab, the innovator reference product approved in the EU (MabThera[®]) will be used as the selected reference medicinal product (RMP) for all study sites participating in this protocol.

The term "biosimilar" refers to a biologic drug that is developed to be similar to an existing approved RMP. Biosimilars are intended to treat the same diseases as the RMP using the same dose and treatment regimen. Unlike generic versions of chemically-synthesised small molecule therapies, biosimilars are not structurally identical to their RMP. This is due to the purity, characteristics, and activity of a specific product being dependent on, and sensitive to changes in the process by which it was manufactured. Therefore, the aim is to create a product with no clinically meaningful differences between the proposed biosimilar and the RMP in terms of pharmacokinetics (PK), safety, immunogenicity, and efficacy.

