9.4.6 Immunogenicity Assessment

Immunogenicity data (BAb and NAb) will be summarised and analysed descriptively for each scheduled protocol assessment time point.

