4.2.2 General Categorical Data Presentation

Categorical data will be summarized in terms of the number of subjects providing data at the relevant time point (n), frequency counts and percentages.

Percentages will be presented to one decimal place. Percentages will be calculated using 'n' (the total number of subjects providing data at the relevant time point) as the denominator.

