4.4.6 Immunogenicity Analysis Set

All randomized subjects with at least one immunogenicity sample with a valid result will be included in the Immunogenicity Analysis Set.

4.4.7 eCRF CCI Risk Category Analysis Set

The eCRF CCI Risk Category Analysis Set will include all subjects from the ITT Analysis Set but with study treatment received (even if different from the randomized study treatment) and CCI risk category as per eCRF (even if different from the category used in the stratified randomization).

4.4.8 eCRF Tumor Grade Analysis Set

The eCRF Tumor Grade Analysis Set will include all subjects from the ITT Analysis Set but with study treatment received (even if different from the randomized study treatment) and tumor grade as per eCRF (even if different from the category used in the stratified randomization).

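### The immunogenicity tables give antibody positivity by visit but do not separate antibodies induced by each product from those present before the first dose

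*SAP*

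**What the plan says.** **Planned summaries.** SAP 4.11.9 describes antibody data at these time points: "baseline, Week 4, Week 8, Week 28, Week 44 and Week 52/EOS or ET". For binding antibodies (BAb) it gives the "Number and percentage of subjects with ADA (binding antibodies (BAb)) results (positive or negative) by treatment group and visit", and the same bullet adds that "for positive subjects, titer values will be summarized". For neutralising antibodies (NAb): "Number and percentage of subjects with NAb results (positive or negative) will be presented by treatment group and visit". A by-subject listing follows. Protocol 9.4.6 says no more than that the data "will be summarised and analysed descriptively for each scheduled protocol assessment time point".

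**Who is counted.** SAP 4.4.6: "All randomized subjects with at least one immunogenicity sample with a valid result will be included in the Immunogenicity Analysis Set". SAP 4.2.2: "Percentages will be calculated using 'n' (the total number of subjects providing data at the relevant time point) as the denominator".

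**What is collected.** Protocol Table 1-1, footnote 20: "Samples for detection of BAb and NAb will be collected before the administration of study drug infusion on Day 1 and Day 22". Protocol 8.3.8 has confirmed BAb-positive samples go on to titre and NAb testing.

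**Other uses of antibody status.** SAP 4.11.2.8 tabulates TEAEs by the BAb result at the EOS/ET visit. Protocol 9.4.4 considers antibody status as a population-PK covariate. SAP 4.2.8 has a general sentence allowing shift tables for categorical data where appropriate.

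**Standing of the endpoint.** Immunogenicity is in the trial title, and comparing it is a secondary objective (Protocol 3, SAP 2.2).

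**The concern.** A biosimilar comparison of immunogenicity asks how often each product provokes antibodies. A percentage positive at a visit answers a different question, because it pools subjects whose antibodies were there before dosing with subjects who developed them on treatment. This blurs the contrast between arms, and a chance imbalance in baseline positivity carries through to every later row.

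Visit rows also give no count of subjects ever positive after dosing. One subject positive only at Week 8 and another positive only at Week 28 appear in different rows and are never combined.

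The SAP applies the baseline principle elsewhere. Under 4.11.2, adverse events that pre-date treatment and do not worsen are not treatment-emergent. Laboratory data, vital signs, ECG and ECOG status have change-from-baseline or shift summaries (4.11.4, 4.11.5, 4.11.7, 4.11.8). Section 4.11.9 has no counterpart, although the Day 1 sample and the titres needed for one are collected.

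**Working it through.** The plan states no figure for immunogenicity (no rate, margin or power), so there is none to reproduce. The check has a textual part and an illustration.

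**Step 1: do baseline positives stay in later percentages?** No sentence says so directly; it follows from two rules. The analysis set (4.4.6) needs one valid sample at any time and sets no condition on baseline. The denominator (4.2.2) is everyone with data at the visit. A subject positive on Day 1 with an unchanged titre is therefore counted positive at each later visit where the result is positive, just like a subject with induced antibodies.

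**Step 2: does another planned output separate the two?**
- Titres are summarised among positives, not as change within a subject.
- The TEAE table (4.11.2.8) uses the EOS/ET result alone, whatever the baseline.
- The population-PK covariate is status only.
- SAP 4.2.8 is discretionary, and 4.11.9 does not invoke it.
- SAP 4.14 lists no change on this point.
- Neither document defines treatment-emergent, induced or boosted antibodies, or plans a cumulative incidence or an arm difference with CI.

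**Step 3: possible size.** From the documents: 156 per arm (SAP 4.13.2). Assumed, because the documents give no rates: baseline prevalence *b* of 2%, 5%, 10% or 20%; induced rates *i* of 5% and 10%; every baseline positive stays positive.

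Mixed prevalence = *b* + (1 − *b*)*i*. At *b* = 5%:
- 0.05 + 0.95 × 0.05 = 0.0975
- 0.05 + 0.95 × 0.10 = 0.145
- ratio 0.145 / 0.0975 = 1.49; difference 4.75 points

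Chance arm difference in baseline positivity, 95% range = ±1.96 × √(2*b*(1 − *b*)/156). At *b* = 5%: 1.96 × √(0.095/156) = 0.048.

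| Baseline *b* | Chance imbalance (points) | Mixed prevalence | Ratio (true 2.0) | Difference (true 5.0 points) |
|---|---|---|---|---|
| 2% | ±3.1 | 6.9% vs 11.8% | 1.71 | 4.9 |
| 5% | ±4.8 | 9.75% vs 14.5% | 1.49 | 4.75 |
| 10% | ±6.7 | 14.5% vs 19.0% | 1.31 | 4.5 |
| 20% | ±8.9 | 24.0% vs 28.0% | 1.17 | 4.0 |

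The ratio is affected much more than the difference.

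**Step 4: precision at *b* = 5%.**
- Mixed prevalence, 156 per arm: 1.96 × √[(0.0975 × 0.9025 + 0.145 × 0.855)/156] = ±7.2 points.
- Induced antibodies only, 156 × 0.95 ≈ 148 baseline-negative subjects per arm: 1.96 × √[(0.05 × 0.95 + 0.10 × 0.90)/148] = ±6.0 points.

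Separating the two sharpens the comparison, but a 5-point difference stays within sampling error.

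**The case against.** The best defence is that the analysis is descriptive and nothing is decided on it: there is no test, margin or planned ratio. Baseline positivity is tabulated by arm, so an imbalance can be seen. The listing would let anyone derive emergent status later. Exclusion criteria 1 and 15 (Protocol 5.2) remove subjects with prior anti-CD20 exposure or known hypersensitivity to murine proteins, so baseline positivity may be low. SAP 4.2.8 leaves room for shift tables.

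Most of this limits the size of the problem without removing it. A baseline row shows how many were positive, not which later positives they became. A status derived from the listing after unblinding would rest on a titre-rise rule chosen with the results in view. Section 4.2.8 commits to nothing here. The exclusions make a low baseline rate plausible but do not establish one.

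Three stronger readings are tempting and should be resisted:
- A reader might infer that visit percentages are all that is reported. The titre summary, the listing and the TEAE-by-antibody table are also planned, though none separates pre-existing from induced antibodies.
- A reader might infer that baseline noise of ±4.8 points is what hides a 5-point difference. Step 4 shows that a clean comparison already carries about ±6.0 points.
- A reader might infer from the ratio that the plan computes a badly biased effect. It computes no ratio, and on the difference scale the loss at 5% baseline prevalence is 0.25 points.

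**Conclusion.** The point stands as a gap in a secondary, descriptive comparison. The planned tables do not isolate antibodies induced by each product and give no cumulative incidence per subject, although the data to do both are collected.

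The size is unknown because no baseline rate is given. Under the stated assumptions, including that baseline positives remain positive (which the documents neither support nor exclude), the mixing is minor near 2% baseline prevalence and material from about 5%, mainly for the ratio and for chance imbalance.

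The documents do not support extending this to the primary endpoint or the equivalence conclusion, neither of which uses antibody status. It is a low-cost improvement worth making before unblinding.

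**What to change.** Add to SAP 4.11.9, before the Week 28 unblinding:

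- **Definitions.** Treatment-induced: BAb negative at Day 1 and positive at any later sample. Treatment-boosted: positive at Day 1 with a post-dose titre rise above an assay-based multiple fixed in advance. Treatment-emergent: either of these.
- **Main table.** Cumulative treatment-emergent BAb incidence to Week 28 and to Week 52 by arm, over subjects with a valid Day 1 result and at least one post-dose sample, with the difference and 95% CI. Report NAb likewise for baseline-negative subjects.
- **Pre-existing antibodies.** Show them separately by arm.
- **Missing Day 1 sample.** Show these subjects separately, with a sensitivity analysis counting them as baseline negative. Counting them as negative in the main table would bring back the mixing that the change is meant to remove.
- **Existing tables.** Keep the per-visit summaries, titres and listing.

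The cost is one additional table per report, from samples already scheduled. The real demand is that the titre multiple, which the documents do not give, must be set from assay data before unblinding.
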